10.5.12 Month 5 (± 7 days) (D0 Visit)

Pre-Injection

- Protocol refraction and visual acuity (4 meters) using ETDRS chart (SE)
- Tonometry and Ophthalmologic examination (SE)
- Spectral Domain optical coherence tomography (SD-OCT) (SE)

Injection

- Zimura™ 2 mg/eye

Post-injection

- Indirect Ophthalmoscopy (SE) – 1 to 2 minutes after the injection to assure that the optic nerve is perfused.

Ophthalmologic exam/Tonometry (SE) – At least 30 minutes after the injection a full ophthalmologic exam must be performed and IOP must be < 30 mmHg before the subject leaves the clinic.

10.5.13 Month 5 (D2 Visit)

Pre-injection

- Protocol refraction and visual acuity (4 meters) using ETDRS chart (SE)
- Tonometry and Ophthalmologic examination (SE)

Injection

- Lucentis® 0.5 mg/eye – administered 1st
 - Indirect Ophthalmoscopy (SE) – 1 to 2 minutes after the injection to assure that the optic nerve is perfused.
 - Ophthalmologic exam/Tonometry (SE) – After the injection, to confirm perfusion of the optic nerve and return of IOP to ≤ 21 mmHg or within 5 mmHg of pre-injection.
- Zimura™ 2 mg/eye – administered 2nd

Post 2nd Injection

- Indirect Ophthalmoscopy (SE) – 1 to 2 minutes after the injection to assure that the optic nerve is perfused.
- Ophthalmologic exam/Tonometry (SE) – At least 30 minutes after the second injection, a full ophthalmologic exam must be performed and IOP must be < 30 mmHg before the subject leaves the clinic.

3-Day Post-Injection Safety Check (± 1 day)

- Telephone call to subject to ensure there are no signs or symptoms of retinal detachment or endophthalmitis.

10.5.14 Month 6 (± 7 days)/Early Withdrawal

- Vital signs
- Laboratory tests
- 12-Lead ECG
- Protocol refraction and visual acuity (4 meters) using ETDRS chart (OU)
- Goldmann applanation Tonometry and Ophthalmologic examination (OU)
- Color fundus photography (FP) (OU)

- Fluorescein Angiography (FA) (OU, transit SE)
- Spectral Domain optical coherence tomography (SD-OCT) (OU)

10.6 Withdrawal from Trial

Subjects have the right to withdraw from the trial at any time for any reason. The Investigator (after consultation with the Sponsor) or Sponsor also have the right to withdraw subjects from the trial in the event of concurrent illness, adverse events, treatment-failure after a prescribed procedure, protocol violations, cure, administrative or other reasons.

Final trial assessments as outlined in the Study Assessments Chart, Section 3, should be performed on all subjects who withdraw. Subjects who withdraw due to an adverse event should be followed until resolution of the adverse event, or an adequate explanation for the event is obtained.

Subjects who withdraw for any reason should have assessments performed according to the Early Withdrawal schedule. If an alternative treatment for NVAMD is initiated before completing the study dosing, the subject will no longer be evaluated according to this protocol.

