10.7 Trial Discontinuation

The reason for a subject discontinuing from the trial will be recorded in the case report form. A discontinuation occurs when an enrolled subject ceases participation in the trial, regardless of the circumstances, prior to completion of the protocol. The investigator must determine the primary reason for discontinuation. A discontinuation must be reported immediately to the clinical monitor or his/her designated representative if it is due to a serious adverse event (SAE) (see Section 12). The final evaluation required by the protocol will be performed at the time of trial discontinuation. The investigator will record the reason for trial discontinuation, provide or arrange for appropriate follow-up (if required) for such subjects, and document the course of the subject's condition.

Premature termination of this clinical trial may occur because of a regulatory authority decision, change in opinion of the IRB/EC, drug safety problems, or at the discretion of Ophthotech Corp.

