12.2 Assessment and Reporting of Adverse Events

Adverse events will be recorded starting after the first dose of trial drug and continuing until 30 days after the last dose or until the last follow-up visit required by the protocol, whichever comes later. An adverse event that is ongoing at the last follow up study visit is required to be followed up until the event resolves or stabilizes at a level acceptable to the investigator and/or Sponsor.

All adverse events spontaneously reported, elicited or observed by the investigators will be recorded. The events will be recorded in the source documents and onto the adverse event pages of the case report form, including date of onset and resolution, severity, relationship to trial treatment and determination of “serious”.

Diagnostic and therapeutic non-invasive and invasive procedures, such as surgery, should not be reported as adverse events. However, the medical condition for which the procedure was performed should be reported if it meets the definition of an adverse event. For example, an acute appendicitis that begins during the adverse event reporting period should be reported as the adverse event, and the resulting appendectomy should be recorded as treatment of the adverse event.

The investigator will take all therapeutic measures necessary for resolution of the adverse event. Any medication necessary for treatment of the adverse event must be recorded in the subject’s source documents and on the appropriate pages of the subject’s case report form.

To assist with grading of adverse event severity, the following definitions are provided:

- Mild** = Aware of sign or symptom, but easily tolerated;
- Moderate** = Discomfort enough to cause interference with usual activity;
- Severe** = Incapacitating with inability to work or do usual activity;

Adverse events are assessed as either related to the intravitreal injection procedure (eyelid speculum, anesthetic drops, mydriatic drops, antibiotic drops, povidone-iodine drops or flush, subconjunctival injection of anesthetic, intravitreal injection), termed “injection procedure-related”, or to study drug (Zimura™ or Lucentis® 0.5 mg).

The relationship to the intravitreal injection procedure or to study drug will be assessed using the following definitions:

- Not Related** = There is not a reasonable possibility that the adverse event is related to the injection procedure or to the study drug.

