12.4 Assessment and Reporting of Serious Adverse Events

Serious adverse events will be recorded starting after the first dose of trial drug and continuing until 30 days after the last dose or until the last follow-up visit required by the protocol, whichever comes later. Any serious adverse event occurring at any other time after completion of the trial must be promptly reported if a causal relationship to trial drug is suspected.

If a serious adverse event occurs, the Sponsor is to be notified within 24 hours of awareness of the event by the investigator. In particular, if the serious adverse event is fatal or life-threatening, notification to the Sponsor must be made regardless of the extent of available adverse event information. This timeframe also applies to additional new information (follow-up) on previously forwarded serious adverse event reports.

**All Serious Adverse Events must be reported to the
Sponsor or Designee within 24 hours.
Refer to the “Safety Contact List” provided separately**

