#### 7.4 ADVERSE EVENTS

Adverse events (AEs) will be recorded starting after the first dose of study drug and continuing until 30 days after the last dose or until the last follow-up visit required by the protocol, whichever comes later.

The safety analyses on AEs will be primarily based on the Treatment-Emergent Adverse Events (TEAEs), which is defined as an AE occurring after the first injection on Day 1 (day of the first dose of study drug) and up to and including 30 days after the last dose of study drug.

All AEs will be coded using MedDRA (Version 21.0) terms.

An overview of TEAEs will be provided. A second overview of TEAEs will be provided which displays the overall summary of TEAEs by the categories ‘Study Eye’, ‘Non-Study Eye’, and ‘Non-Ocular’. In addition, the number and percentage of patients with TEAEs will be tabulated for each treatment group and in total by system organ class (SOC) and preferred term (PT). The number and percentage of the subjects who experienced at least one TEAE will be included. Subjects will only be counted once for each preferred term. In case that a subject experienced the same event more than once, the worst severity will be presented.

Tabular summaries of the following AEs will be provided by SOC and PT:

- All TEAEs regardless of the relationship to study drugs
- All TEAEs (regardless of the relationship to study drugs) with PT occurring  $\geq 5\%$  frequency based on total subjects
- TEAEs related to study drugs
- TEAEs related to injection procedure
- TEAEs by the maximum severity grade
- Systemic TEAEs
- Systemic TEAEs related to study drugs
- Systemic TEAEs related to injection procedure
- TEAEs related to study drugs by the maximum severity grade
- TEAEs related to injection procedure by the maximum severity grade
- All Ocular TEAEs by study eye
- All Ocular TEAEs by fellow eye
- Study drug related Ocular TEAEs by study eye
- Study drug related Ocular TEAEs by fellow eye
- Injection procedure related Ocular TEAEs by study eye
- Injection procedure related Ocular TEAEs by fellow eye
- Ocular TEAEs (study eye) by the maximum severity grade
- Study drug related Ocular TEAEs (study eye) by the maximum severity grade
- Injection procedure related Ocular TEAEs (study eye) by the maximum severity grade
- TEAEs leading to discontinuation of study drug
- Study drug related TEAEs leading to discontinuation of study drug
- Injection procedure related TEAEs leading to discontinuation of study drug

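### Protocol 10.6 ends evaluation when alternative NVAMD treatment starts early, leaving it unclear whether new adverse events are still recorded to day 30 after the last dose

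*Protocol*

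**What the plan says.** Protocol 10.6 closes with the sentence "If an alternative treatment for NVAMD is initiated before completing the study dosing, the subject will no longer be evaluated according to this protocol". It makes no exception for safety data and does not say which eye is meant. The same section also provides: "Final trial assessments as outlined in the Study Assessments Chart, Section 3, should be performed on all subjects who withdraw". It adds: "Subjects who withdraw for any reason should have assessments performed according to the Early Withdrawal schedule". Subjects who leave because of an AE are to be followed until that event resolves or is explained.

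The safety sections set a window that runs from the dosing dates. Protocol 12.2 states: "Adverse events will be recorded starting after the first dose of trial drug and continuing until 30 days after the last dose", or to the final protocol visit if that is later. Protocol 12.4 gives SAEs the same window: "Serious adverse events will be recorded starting after the first dose of trial drug and continuing until 30 days after the last dose". Neither mentions subjects who start another treatment. SAP 7.4 defines treatment-emergent events as running "up to and including 30 days after the last dose of study drug", and SAP 7.1 defines treatment duration as last injection date minus first injection date plus 31.

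Protocol 9.3 allows NVAMD treatment of the fellow eye with an approved product at any time, and also allows Avastin® there at the investigator's discretion.

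**The concern.** Safety is the trial's only objective (Protocol 5.1), so the period over which events are collected determines what the trial can report. A site that follows 10.6 to the letter would stop recording when alternative treatment starts. A site that follows 12.2 and 12.4 would continue to day 30 after the last dose. Two sites could therefore handle the same patient differently, and both could cite the protocol.

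The analysis would not show the difference. SAP section 7 uses observed cases without imputation, so a subject whose later event was never recorded would be tabulated as having had no such event. The exposure formula in SAP 7.1 would still credit that subject with the full 30 days after the last injection.

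**Working it through.** The plan states no figure for this point, and Protocol 11.4.1 gives no formal sample size calculation, so there is nothing to reproduce. The check sets the passages side by side and then measures the gap.

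**Step 1. What covers a subject who switches before completing study dosing?**

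| Event | Provision that captures it | Still in force if 10.6 is read literally? |
|---|---|---|
| AE that caused withdrawal | 10.6, follow-up to resolution or explanation | Yes |
| AE found at the Early Withdrawal visit | 10.6 and 10.7, final assessments | Yes, unless the closing sentence of 10.6 is taken to override the visit |
| AE ongoing at the last visit | 12.2, followed until resolved or stable | Yes |
| SAE after completion of the trial, suspected to be related | 12.4, prompt reporting | Yes |
| New AE between the switch and day 30 | 12.2 window only | In doubt |
| New SAE between the switch and day 30 | 12.4 window only, apart from the late-report clause above | In doubt |

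Protocol 10.7 also has the investigator arrange follow-up where required and document the subject's course. It sets no schedule or duration for this, so it does not settle the last two rows.

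**Step 2. Which days does the analysis count?** The SAP 7.1 formula is last − first + 31 = (last − first + 1) + 30. The term in brackets counts the days from first to last injection inclusive. The remaining 30 are the days after the last injection, the same length as the SAP 7.4 tail.

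**Step 3. Length of the gap.** Let k be the days from last study dose to alternative treatment, with k no more than 30. Days in doubt = 30 − k.

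| k | 30 − k | Share of the 30 days |
|---|---|---|
| 0 | 30 | 100% |
| 7 | 23 | 23/30 = 77% |
| 14 | 16 | 16/30 = 53% |
| 21 | 9 | 9/30 = 30% |
| 28 | 2 | 2/30 = 7% |

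A subject on monthly dosing who switches at about the time of the next due visit therefore loses about two days or none.

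**Step 4. Scale in cohorts of this size.** One subject-level event is 1/10 = 10 percentage points in Cohorts 1 and 2, and 1/20 = 5 points in Cohorts 3 and 4. This is only the granularity of the tables, not an estimate of bias.

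For an outer illustration, assume that 0% to 20% of subjects switch and treat each switcher as wholly unobserved, which is harsher than the text. With an assumed true event rate of 10%, the chance of seeing at least one event is 1 − 0.9^n. With no events seen, the one-sided 95% upper limit is 1 − 0.05^(1/n).

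| Observed n | Chance of at least one event | Upper limit if none |
|---|---|---|
| 10 (none lost) | 65.1% | 25.9% |
| 8 (20% lost) | 57.0% | 31.2% |
| 20 (none lost) | 87.8% | 13.9% |
| 16 (20% lost) | 81.5% | 17.1% |

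**Step 5. Which eye?** The 10.6 sentence refers to alternative NVAMD treatment without naming an eye, while 9.3 permits such treatment in the fellow eye. Read literally, a permitted fellow-eye injection could be taken to end evaluation.

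**The case against.** The strongest reply is that 10.6 was never meant to touch safety reporting. Section 10 uses the word evaluations for the visit schedule in the Study Assessments Chart, and the sentence directly follows one about Early Withdrawal assessments. AE and SAE recording has its own sections, with a window tied to the last dose and no exception for switchers. Ending scheduled evaluation after an off-protocol treatment is also a defensible choice in a small, descriptive, open-label study. This reading is reasonable, but the text does not state it, and the chart itself carries an adverse-event row, so a site could equally conclude that event collection stops too.

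It is also fair that every early withdrawal has a single Early Withdrawal visit and nothing scheduled afterwards. Most of the difference in follow-up between completers and non-completers therefore comes from withdrawal itself, not from this sentence.

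A reader might go further and infer that 10.6 removes safety follow-up altogether, and does so in the subjects most likely to have been harmed. The documents do not support that. Protocol 10.7 adds its own requirement: "The final evaluation required by the protocol will be performed at the time of trial discontinuation". The other provisions in Step 1 also remain, so the effect is confined to new events in a short interval. No section gives reasons for switching. It may reflect insufficient response, which Protocol 12.1 excludes as an AE, and subjects who leave because of an AE have their own follow-up rule.

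**Conclusion.** The conflict is real on a literal reading and should be resolved, but it is narrow. It concerns only subjects who start alternative NVAMD treatment before completing study dosing, and only new AEs and SAEs between that start and day 30 after the last dose. Its length is 30 − k days: substantial for a switch within one or two weeks of the last dose, and negligible near four weeks.

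The number of switchers, their timing and their reasons are not given. The size of any under-count is therefore unknown, and so is whether it would fall more heavily on one cohort. The 0% to 20% range and the 10% event rate above are assumptions, not features of the plan. The mismatch with 9.3 over the eye is a separate ambiguity in the same sentence.

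**What to change.** Reconcile 10.6 with 12.2, 12.4 and 9.3 by replacing its closing sentence. Possible wording:

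*Starting another treatment for NVAMD in [eye to be specified, consistent with 9.3] before study dosing is complete ends the scheduled study evaluations. The Early Withdrawal assessments still apply. AEs and SAEs continue to be recorded for the period given in 12.2 and 12.4, by telephone if needed. The start date of the other treatment is recorded.*

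Add a line to SAP 7.4 so that events with onset after that date are flagged in the listings.

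This concerns data collection only. It does not say when alternative treatment may be given or in what order it and the assessments should occur. The sponsor must decide which eye is meant.

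The cost is one protocol sentence, one SAP line and a telephone contact for each subject who switches. The downside is small: events after the switch are partly confounded by the new treatment, which is why they need the flag.

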10.7 Trial Discontinuation

The reason for a subject discontinuing from the trial will be recorded in the case report form. A discontinuation occurs when an enrolled subject ceases participation in the trial, regardless of the circumstances, prior to completion of the protocol. The investigator must determine the primary reason for discontinuation. A discontinuation must be reported immediately to the clinical monitor or his/her designated representative if it is due to a serious adverse event (SAE) (see Section 12). The final evaluation required by the protocol will be performed at the time of trial discontinuation. The investigator will record the reason for trial discontinuation, provide or arrange for appropriate follow-up (if required) for such subjects, and document the course of the subject's condition.

Premature termination of this clinical trial may occur because of a regulatory authority decision, change in opinion of the IRB/EC, drug safety problems, or at the discretion of Ophthotech Corp.

11 STATISTICAL METHODS

11.1 Experimental Design

There will be 4 dosing cohorts in this trial. Approximately 60 subjects will be enrolled; 10 subjects in cohorts 1 and 2, and 20 subjects in cohorts 3 and 4.

Cohort 1

Administered for a total of 6 times (Day 1 – Month 5), in the following sequence, 2 days apart:

- D0: Lucentis[®] 0.5 mg/eye
- D2: Zimura[™] 4 mg/eye (administered as two injections of Zimura 2 mg)

Cohort 2

Administered for a total of 6 times (Day 1 – Month 5), in the following sequence:

- Lucentis[®] 0.5 mg/eye followed by Zimura[™] 2 mg/eye on the same day

Cohort 3

Induction Phase: Administered for a total of 3 times (Day 1 – Month 2), in the following sequence, 14 days apart:

- D0: Lucentis[®] 0.5 mg/eye followed by Zimura[™] 2 mg/eye on the same day
- D14: Zimura[™] 2 mg/eye

Maintenance Phase: Administered for a total of 3 times (Month 3 - Month 5), in the following sequence:

- Lucentis[®] 0.5 mg/eye followed by Zimura[™] 2 mg/eye on the same day

Cohort 4

Induction Phase: Administered for a total of 3 times (Day 1 - Month 2), in the following sequence, 14 days apart:

- D0: Lucentis[®] 0.5 mg/eye followed by Zimura[™] 2 mg/eye on the same day
- D14: Zimura[™] 2 mg/eye

Maintenance Phase: Administered for a total of 3 times (Month 3 - Month 5) in the following sequence, 2 days apart:

- D0: Zimura™ 2 mg/eye
- D2: Lucentis® 0.5 mg/eye followed by Zimura™ 2 mg/eye on the same day

All subjects will have a final follow-up visit at Month 6.

The first 10 subjects will be enrolled into Cohort 1 according to the procedures noted below.

The first three subjects will be assigned to Cohort 1 (Lucentis® 0.5 mg and Zimura™ 4 mg). Once the 3rd subject completes a safety period of one week after the first dose of Zimura™ 4 mg without the occurrence of a dose limiting toxicity as defined in Section 9.2.3 Dose Limiting Toxicity, full enrollment of Cohort 1 may commence.

If a DLT occurs in one or more of the first 3 subjects assigned to Cohort 1, then the Ophthotech medical team will evaluate all available data and either discontinue Cohort 1 or enroll an additional three subjects (for a total of 6 subjects) in Cohort 1. If the three additional subjects are enrolled, and no additional DLT occurs once the second set of 3 subjects in Cohort 1 has reached one week after the first dose of Zimura™ 4 mg/eye, full enrollment of Cohort 1 may commence. If one or more DLTs occur in the second set of 3 subjects, a discussion of safety data will be held among the Ophthotech medical team to review the observed toxicities and determine whether Cohort 1 may proceed.

Once Cohort 1 has been fully enrolled, or if enrollment has been stopped due to one or more DLTs, then enrollment in the remaining 3 cohorts may commence. Subjects will be randomized in a 1:2:2 ratio to Cohort 2, Cohort 3, or Cohort 4.

11.2 Randomization

Once all subjects have been enrolled in cohort 1, subjects will be centrally allocated to one of the three remaining treatment cohorts using a randomization list generated by a block randomization.

11.3 Endpoints

Safety Endpoints:

Safety endpoints include adverse events, vital signs, electrocardiography readings (ECG), ophthalmic variables [visual acuity, intraocular pressure (IOP), ophthalmic

examination, stereoscopic fundus photography, fluorescein angiography (FA), spectral domain optical coherence tomography (SD-OCT)], and laboratory variables.

11.4 Number of Subjects

Approximately 60 subjects will be enrolled, 10 subjects in cohorts 1,2 and 20 subjects in cohorts 3, 4.

11.4.1 Sample Size Required

As this study is not designed to perform formal hypothesis testing, there is no formal sample size calculation. The sample size selected is based on a reasonable number of subjects to understand the safety variables of the proposed regimen and to improve upon the study design prior to performance of controlled trials that may be initiated in the future.

11.4.2 Statistical Analyses

No formal hypothesis testing will be performed.

11.4.3 Descriptive Statistics

Descriptive statistics will be provided to document Baseline and on-trial comparability, including demographic information, treatment administration, and protocol violations.

